7.6 Exploratory Analyses of the Primary Outcome

- a) **Differential practice effects by recruitment source:** The study recruited participants from ARIC and from a community sample. ARIC participants have had prior exposure to testing while non-ARIC participants have not. To address this potential limitation, we will use a mixed effects modeling framework to examine practice effects using an indicator for the first visit in each condition, allowing the practice effect parameter to vary by recruitment source and keeping the estimated intervention effect constant. We will test the fit of that model to one where the intervention effect differs by condition to evaluate whether differential practice effects by recruitment source affects the intervention condition difference. This is a test of effect modification.
- b) Does intervention alter the trajectory of cognitive decline: In the subset of ARIC participants, we will model prior cognitive change (before the baseline ACHIEVE visit) as well as prospective change through study end (2021-22) using linear spline models, to determine if the rate of change of cognitive decline during ACHIEVE in each condition is different than the rate of change in the preceding years in ARIC visit 5 and 6. We will also test the interaction hypothesis that the hearing intervention deceleration in decline is larger than that in the successful aging intervention condition. The power for analyses in the ARIC subgroup will be lower than optimal since the proportion of ACHIEVE participants recruited from ARIC was smaller than originally anticipated.
- c) **Subgroup analyses by demographics:** Given the lower prevalence of hearing loss in women compared to men and blacks compared to other races, an exploratory analysis will be conducted stratifying by sex, race, and education. We will also conduct analyses stratifying by level of hearing loss and level of baseline global cognitive function factor score. Interactions between intervention condition and subgroups will be tested in additional models relative to p < 0.10.

- d) Subgroup analyses by AD risk factors: We will investigate a further refinement of the primary analysis with subgroup analysis for known AD risk factors, including but not limited to ≥ 1 APOE ε4 allele as well as diabetes or hypertension. A subset of ARIC participants will be defined as more likely to be at high risk of AD based on reduced temporal lobe volume meta ROI²⁷ by structural MRI and no small vessel disease (ARIC Visit 5, 2011-13).
- e) **Exclusion of tests with only auditory stimuli:** Among the full study cohort, we will derive a revised global cognitive function factor score excluding tests with only auditory stimuli (logical memory test and digit span backwards). We will use model constraints in a latent variable modeling framework to scale these revised factor scores to be on the same metric as the factor scores in the primary analysis²⁷.
- f) Mediation by social function: We will investigate the extent to which cognitive improvements are mediated by improvements *in social function* using causal mediation methods²⁸.

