4.1 Inclusion Criteria

To be eligible for the study, participants must meet all of the following criteria:

- Age 70-84 years at the time of randomization. This age range will allow recruitment of participants who are at risk for cognitive decline but who may also be expected to survive for the duration of the study.
- Community-dwelling.
- Fluent English-speaker.
- Residency. Participants must plan to reside in the local area for the study duration.
- Audiometric hearing impairment. Participants must have adult-onset hearing impairment with a four-frequency pure tone average (0.5, 1, 2, 4 kHz) in the better-hearing ear of ≥ 30 decibels and <70dB. This level of hearing impairment is the level at which individuals would be most likely to benefit from the use of conventional amplification devices such as hearing aids.
- Word recognition in quiet score ≥60% in better ear. A word recognition in quiet score <60% suggests hearing impairment that is too severe to benefit from conventional amplification devices such as hearing aids.
- Mini-Mental State Exam (MMSE) score ≥ 23 for individuals with high-school degree or less; MMSE score ≥ 25 for individuals with some college or more; Participants must be at risk for cognitive decline in the range quantified well by neurocognitive testing, and so must be free from more substantial cognitive impairment at baseline.

Participants must be willing and able to consent to participate in the study, be willing to be randomized to either the hearing intervention or to the successful aging control intervention and be willing to commit to adhere to the protocol for the duration of the study.

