5.2 Evaluation of Assumptions

An assumptions analysis took place in June 2019, prior to the closure of the initial recruitment period. The goal of the analysis was to evaluate a subset of the assumptions described above and assess the value of a possible increase in the sample size. Since ACHIEVE was not going to be stopped early for efficacy or futility, regardless of the interim results, and the interim analysis only investigated assumptions around attrition and drop-in/drop-out rates, not outcomes, the interim analysis did not lead to increased type I error rates. Moreover, it was important to determine the extra required sample size, if any, as soon as possible in order to promptly begin the second stage of recruitment and expand the sample while there were still active participants from the initial stage.

Both the attrition rate and the drop-in/drop-out rate were examined based on 1 year follow-up data from approximately 200 participants. The data suggested that the original assumptions made in the sample size calculations were reasonable. However, there was potential variability in the estimates since partial data were used in the analysis. Consequently, the DSMB recommended increasing the sample size up to 1000 participants. The final sample size is 977 participants. This increased sample provided additional power for all tests, including greater than 90% power to detect a difference in cognitive decline after accounting for the estimated attrition and drop-in/drop-out rate as well as 80% power to detect a hazard ratio of 0.60 in the proportional-hazards analysis of incident cognitive impairment.

6. Analysis Populations

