7.1 General Considerations

Study data will be monitored on an on-going basis by the ACHIEVE Data Coordinating Center (DCC). The DCC will send data clarification requests to the clinical sites for resolution while the study is on-going. Final cleaning and editing of the study database will be carried out after the final participant completes their last follow-up visit. Unblinding of treatment assignments will not be performed until the study data are cleaned, queries resolved, and database lock achieved. A permanent archive of the database will be maintained by the DCC. Randomization, stratified by ARIC study status, center, and hearing impairment level is completed within CDART, the DCC's data management system. Built-in algorithms first check for missing key items and eligibility criteria, reducing protocol violations associated with enrollment. Although the ACHIEVE hearing aid intervention is, by nature, un-masked, to minimize bias based on review of accumulating data by the project team, the ACHIEVE PI, co-investigators, and key project staff, except for key data coordinating center staff, will remain blinded to accumulating data. This will be done by applying a dummy ID onto the treatment-specific data forms as they are transferred from CDART to SAS for data cleaning and interim reporting.

This statistical analysis plan (SAP) was developed prior to review of the study dataset and under the assumption that all data were collected in adherence to the protocol and in accordance with good clinical research practices. As the data are analyzed, some deviation is anticipated (e.g., missing data; small sample sizes). In instances where these deviations would make the proposed analyses inappropriate, modifications to the analysis plan will be made and noted in the final report.

Consistent with best practices in clinical trials, we will assess the comparability of the randomized conditions with respect to known baseline confounders, such as hearing loss (pure tone average in the better hearing ear <40 db vs 40+ db), recruitment source (ARIC vs de novo), center, age, sex, education, and the presence of APOE ε 4 alleles⁶. If, despite randomization, there is an imbalance between the treatment conditions we will adjust for relevant confounders as well as explore the use of a precise, locally efficient, augmented, simple estimator⁷ which may offer greater precision.

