7.2 Primary Outcome

The primary outcome is cognitive decline, as measured by the change in a global cognitive function factor score. The factor score is derived from a confirmatory factor analysis model that identifies common covariation among all cognitive tests administered in-person. Factor scores are generated for each participant at each in-person assessment using a measure harmonization and item banking approach^{16, 17}. Factor loadings and latent means for each neurocognitive test are estimated using data from the ACHIEVE baseline. The mean of the global cognitive function factor score at the baseline is set to 0 and the SD is set to 1. Fixed parameter estimates from the baseline model are then integrated into models that estimate the factor mean and SD at each subsequent assessment. This process ensures that changes over time represent changes in the underlying factor rather than changes in the scaling or meaning of the constructs. The assumption of longitudinal measurement invariance is supported by prior studies that utilized similar neurocognitive tests^{18, 19}. A final fixed parameter model analyzes available data collected in-person and

computes a global cognitive function factor score for each participant at every assessment in which one or more neurocognitive tests were completed. A comparable process is used to generate factor scores for the cognitive domains of memory, executive functioning, and language.

7.3 **Primary Analysis**

We will examine cognitive decline within each condition using mixed effects models that account for the correlation among repeated measures as well as the correlation between spouses or cohabitating partners. If a linear trend appears reasonable, we will fit a model with a linear slope. If a nonlinear trend is observed, the model will be adapted to include time splines²⁰. Continuous time in years from the baseline will be the time scale. An interaction term between treatment assignment and time will be used to test if rates of cognitive change differ by treatment assignment. Model fit will be assessed with residual plots and other statistics (Akaike Information Criterion, Bayesian Information Criterion, etc.). The primary analysis may include adjustments for the baseline hearing loss, ARIC vs de novo status, center, age, sex, education, and APOE ϵ 4 alleles.

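### Effect modification by hearing loss and baseline cognition is tested only through levels of two continuous measures; if benefit changes roughly linearly, this costs power by an amount that depends on cuts the plan does not fully define

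*SAP*

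**What the plan says.** SAP 7.6(c) puts demographic subgroups first ("an exploratory analysis will be conducted stratifying by sex, race, and education") and then adds the two moderators at issue: "We will also conduct analyses stratifying by level of hearing loss and level of baseline global cognitive function factor score". The test follows: "Interactions between intervention condition and subgroups will be tested in additional models relative to p < 0.10". Protocol 12.2, exploratory analysis (c), plans the same.

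Both measures are continuous:

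- **Hearing.** Eligibility in SAP 4.1 requires a four-frequency average "in the better-hearing ear of ≥ 30 decibels and <70dB". For analysis, SAP 7.1 groups it as "pure tone average in the better hearing ear <40 db vs 40+ db". Protocol section 8 uses the same 40 dB boundary as the mild/moderate randomisation stratum. Spouse or partner pairs are the exception: they are stratified by ARIC status and site only.
- **Cognition.** SAP 7.2 scales the score: "The mean of the global cognitive function factor score at the baseline is set to 0 and the SD is set to 1". For this analysis, neither document gives a number of levels or a cut-point.

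Neither document describes an interaction with either measure in continuous form, and neither states a power or an effect size for any interaction test.

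**The concern.** These analyses ask whether people with worse hearing, or with lower cognition at entry, gain more from the hearing intervention. If benefit rises gradually, a test on levels treats 30 and 39 dB as the same and 39 and 41 dB as different, and so throws away part of the gradient. Interaction tests have little power to begin with. A real gradient would then be more likely to be reported as absent, although the continuous values are baseline measurements that the trial already collects.

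**Working it through.** **Inputs from the documents**

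- Randomised: "The final sample size is 977 participants" (SAP 5.2), 1:1 (Protocol 8).
- SD of 3-year change 0.27; control decline 0.24 SD over 3 years; net drop-in/drop-out 15% (Protocol 12.1).
- Attrition 27.1% over 3 years as planned; 6.7% observed by October 2021 (SAP 5.1).
- Planned difference 35%, so 0.35 × 0.24 = 0.084 at 3 years. The SAP's diluted difference is 3 × (0.080 − 0.057) = 0.069.
- Interaction alpha 0.10. The text does not say one- or two-sided; two-sided is assumed.

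**Inputs assumed, because the documents give none:** the interaction effect per SD of moderator, the shape of each moderator's distribution, the share at or above 40 dB, and the cut(s) for the cognitive score.

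**Step 1. Reproduce the plan's own power** (two-sample comparison, two-sided 0.05)

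- N = 850, 425 × 0.73 = 310 per arm, difference 0.85 × 0.084 = 0.0714: 90.9% (stated 90%).
- N = 850, difference 0.069: 88.9% (stated above 80%).
- N = 977, difference 0.069: about 92.6% (stated above 90%).

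The planning inputs are therefore a sound basis for the next steps.

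**Step 2. Information kept by a cut**

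For a normal moderator, a linear interaction and one cut at proportion p, the share kept is φ(z_p)² / [p(1 − p)]. For k ordered levels scored as a trend, it is the between-level variance divided by the total variance. The largest power loss is the maximum over d of power(d) − power(d√share), where power(d) = Φ(d − 1.645) + Φ(−d − 1.645).

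| Grouping | Information kept | Largest power loss, alpha 0.10 |
|---|---|---|
| Median split | 63.7% | 16.8 points (76.3% to 59.4%) |
| One-third / two-thirds | 59.5% | 19.3 points |
| One-quarter / three-quarters | 53.9% | 22.9 points |
| Tertiles as a trend | 79.3% | 8.7 points |
| Quartiles as a trend | 86.1% | 5.7 points |

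Tertiles tested as unordered groups (2 df) lose up to 18.4 points.

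**Step 3. The 40 dB cut**

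The cut was applied to truncated-normal and uniform distributions on 30–70 dB. With roughly 20% to 80% of participants at or above 40 dB, it loses about 32% to 52% of the information, and at most about 15 to 27 points of power.

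**Step 4. Power on this trial's numbers, median split**

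The standard error of the interaction per SD of moderator is 2 × 0.27 / √n. With n = 977 × 0.729 = 712 it is 0.0202; with n = 977 × 0.933 = 912 it is 0.0179.

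| Assumed effect per SD | n | Continuous | Median split |
|---|---|---|---|
| 0.021 | 712 | 27.6% | 21.4% |
| 0.0345 (half of 0.069) | 712 | 52.4% | 38.9% |
| 0.042 (half of 0.084) | 712 | 66.7% | 50.5% |
| 0.063 | 712 | 92.9% | 79.9% |
| 0.042 | 912 | 75.9% | 59.1% |

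A simulation at n = 712 and 0.049 per SD gave 76% against 60%, in line with the formula.

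**Step 5. The opposite case**

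If the true effect is a step exactly at the cut, the two-level test loses nothing. The same squared correlation then works against the linear term: for a step at the median, the linear test would be the one keeping 64%.

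**The case against.** The strongest reply is that the 40 dB grouping is part of the design. It is a randomisation stratum for individually randomised participants, was fixed before any data, cannot be moved after results are seen, and assumes no functional form. That stands as a reason to keep it as a covariate and for display. It does not make it the best sole form of the moderator when benefit may be graded.

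The size is also conditional. The documents specify no median split, no number of cognitive levels and no share at or above 40 dB. A reader might take a loss of one third of the information, or 17 points, as a property of this plan or as an upper limit. It is neither, as Steps 2 and 3 show. The interaction effects are assumptions too.

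Three further inferences are tempting but unsupported:

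- **That the cognitive cut will be picked after seeing results.** SAP section 8 says cut-points for clinically relevant impairment already exist for the general cognitive performance factor score. SAP 7.6(c) does not say they will be used, so all that can be said is that the levels are unspecified.
- **That these two moderators are a named trial objective.** The exploratory objective in SAP section 3 covers demographics, biomarkers and Alzheimer's disease risk factors. It names neither hearing level nor baseline cognition.
- **That a trial conclusion is at risk.** The analyses are labelled exploratory and lie outside the multiplicity procedure in SAP 7.7.

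**Conclusion.** The point holds as a modest improvement to an exploratory analysis. Both moderators are continuous, the plan tests them only through levels, and the levels of the cognitive score are not defined. Under a roughly linear gradient, a median split of a normal moderator keeps 64% of the information and costs at most about 17 points at two-sided alpha 0.10. The loss reaches about 23 points for a quarter/three-quarters cut and falls to about 9 or 6 points for three or four ordered levels tested as a trend. The 40 dB cut loses about 32–52% of the information over the distributions tried. With a true step at the cut there is no loss.

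These figures use the planning SD and attrition in a simple 3-year change comparison; they do not model the repeated measures, the imputation or the pairing of spouses. No primary or secondary conclusion changes.

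**What to change.** In SAP 7.6(c) and Protocol 12.2(c), for these two moderators only:

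1. Base the exploratory interaction test on condition × time × continuous moderator, using the better-ear pure-tone average and the baseline factor score, with all lower-order terms. The three-way term is needed because the planned treatment effect in SAP 7.3 is itself condition × time.
2. Carry the same terms in the imputation model of SAP 7.3, so that imputed scores do not dilute the interaction.
3. Add a quadratic or spline check of linearity.
4. Keep the <40 / 40+ dB strata to display estimates, and define the factor-score levels in advance for the same purpose.

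Cost: a short change of wording and a few more model terms per moderator, with no new data. The downside is the assumption of a roughly linear gradient, which the curvature check addresses; the displayed strata would also help to reveal a step.

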7.7 Adjustment for Multiple Comparisons

Statistical significance for the primary outcome will be defined as p < 0.05. Secondary outcomes will be evaluated for statistical significance with a Hochberg modification to the Bonferroni adjustment, in which the p-values of the five outcomes will be ordered. The largest p-value will be compared relative to p < 0.05, and if met, all parameters will be considered significant. If not, then the second largest p-value will be assessed relative to p < 0.05/2 = 0.025, and if met then it and all other parameters will be considered significant, and so on for the 3rd p-value compared at 0.05/3=0.017, the fourth compared to 0.05/4 = 0.012, and the fifth compared to 0.05/5 = 0.01.

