### **Adjustment for Multiple Comparisons**

Statistical significance for the primary outcome will be defined as  $p < 0.05$ . Secondary outcomes will be evaluated for statistical significance with a Hochberg modification to the Bonferroni adjustment, in which the p-values of the five outcomes will be ordered. The largest p-value will be compared relative to  $p < 0.05$ , and if met, all parameters will be considered significant. If not, then the second largest p-value will be assessed relative to  $p < 0.05/2 = 0.025$ , and if met, then it and all other parameters will be considered significant, and so on for the third p-value compared to  $0.05/3 = 0.017$ , the fourth compared to  $0.05/4 = 0.012$ , and the fifth compared to  $0.05/5 = 0.01$ .

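### The written Hochberg rule, read literally, also declares significant the outcomes that have just failed their own cut-off

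*SAP*

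**What the plan says.** SAP 7.7 gives the primary outcome its own criterion: "Statistical significance for the primary outcome will be defined as p < 0.05". It then sets the rule for the rest: "Secondary outcomes will be evaluated for statistical significance with a Hochberg modification to the Bonferroni adjustment". Five p-values enter the ordering.

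The steps are as follows.

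- **Step 1:** "The largest p-value will be compared relative to p < 0.05, and if met, all parameters will be considered significant".
- **Step 2**, reached only if step 1 fails: the second largest p-value is compared with 0.025, "and if met then it and all other parameters will be considered significant".
- **Later steps:** "and so on for the 3rd p-value compared at 0.05/3=0.017", then "the fourth compared to 0.05/4 = 0.012", and the fifth at 0.01.

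The matching paragraph in Protocol 12.2 has the same rule: "and if met, then it and all other parameters will be considered significant". Neither document restricts the declaration to outcomes with smaller p-values.

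**The concern.** Step 1 is right: if the largest p-value is below 0.05, every outcome is declared. Step 2 is reached only because the largest p-value was not below 0.05. A rule that then declares every other outcome takes in the one that has just failed. Carried through the later steps, a single p-value below 0.01 would make all five outcomes significant, whatever the other four showed.

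This is the only multiplicity rule for the secondary outcomes (the time-to-impairment composite, memory, executive function and language). SAP 7.5 places their results in the primary manuscript, and the remaining outcomes are exploratory and unadjusted. A program written from this sentence could report a null secondary outcome as a significant finding.

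**Working it through.** **Inputs from the documents.** There are five ordered p-values with cut-offs 0.05/k for k = 1 to 5 (SAP 7.7). The SAP's table of changes from version 5.1 to 5.2 lists the five as global cognition plus the four secondary outcomes.

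**Cut-offs.** 0.05/1 = 0.05; 0.05/2 = 0.025; 0.05/3 = 0.016667; 0.05/4 = 0.0125; 0.05/5 = 0.01. The printed 0.05, 0.025 and 0.01 are exact. The printed 0.017 is 0.016667 correctly rounded to three decimals. 0.0125 is a tie at three decimals, and the printed 0.012 is its lower, stricter rounding.

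**The two rules.** Let step k be the first at which the k-th largest p-value is below 0.05/k.

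- *Hochberg:* declare that outcome and all with smaller p-values.
- *Literal text:* declare that outcome and all the others, so all five.

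**Example 1.** p = 0.60, 0.02, 0.015, 0.008, 0.004. Step 1: 0.60 is not below 0.05. Step 2: 0.02 < 0.025, met. Hochberg declares four outcomes and leaves out 0.60. The literal text declares five.

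**Example 2.** p = 0.60, 0.40, 0.30, 0.20, 0.004. Steps 1 to 4 fail. Step 5: 0.004 < 0.01, met. Hochberg declares one outcome and the literal text declares five.

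**Family-wise error by simulation.** The assumptions are five two-sided z-tests, a common correlation, and real effects with mean z = 1.960 + 1.282 = 3.242 (90% power at 0.05). There were 500,000 runs with exact cut-offs. Entries are the chance of declaring at least one null outcome, Hochberg / literal.

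| Scenario | Correlation 0 | Correlation 0.5 |
|---|---|---|
| Five nulls | 0.0488 / 0.0488 | 0.0423 / 0.0423 |
| One real effect, four nulls | 0.0469 / 0.7580 | 0.0408 / 0.7616 |
| One very large effect, four nulls | 0.0491 / 1.0000 | 0.0438 / 1.0000 |
| Two real effects, three nulls | 0.0451 / 0.9390 | 0.0389 / 0.8884 |
| Four real effects, one null | 0.0408 / 0.9962 | 0.0360 / 0.9525 |

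A separate simulation (400,000 runs, correlations 0.3, 0.5 and 0.7) agrees. With one real effect it gives 0.045, 0.040 and 0.035 under Hochberg against 0.760, 0.761 and 0.762 under the literal text. With four real effects and one null it gives 0.039, 0.036 and 0.032 against 0.976, 0.952 and 0.916.

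**Check by hand.** Under the literal text, the nulls are all declared whenever the one real outcome has p < 0.01, because a step is then met at the fifth at the latest. That probability is about Φ(3.242 − 2.576) = Φ(0.666) ≈ 0.747, a floor consistent with the simulated 0.758.

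**Why the rules agree when nothing is real.** With five nulls, any declaration is a false one, so both error rates equal the chance that some step is met.

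**Effect of the printed decimals.** Under standard Hochberg with the printed cut-offs, the simulated family-wise error is at most 0.0494 in all these scenarios.

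**The case against.** The strongest reply is that the plan names its method. It orders the p-values, starts from the largest and moves on only after a failure. In that sequence the other parameters can be taken as those still to be tested. The literal reading would also make the result all-or-nothing, so ordering five outcomes could never separate one from another. A statistician who recognises Hochberg would not declare p = 0.60. This stands as evidence of intent, and the error rates near 76% and above describe literal application only. It does not mend the sentence. Version 5.2 of the SAP was issued to clarify this paragraph, and SAP section 10 has analyses programmed from written requests, so the written rule should be correct as it stands.

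A reader might infer three stronger things that the documents do not support.

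- *That the analysts intend the all-or-nothing rule.* Nothing shows this, and the named procedure points the other way.
- *That the primary conclusion is at risk because global cognition is among the five.* SAP 7.7 opens by giving the primary outcome its own 0.05 criterion, which does not depend on the later steps.
- *That two cut-offs are mis-rounded.* 0.017 is correct to three decimals. 0.012 is a slightly strict rounding of a tie. Both are printed beside their exact fractions, and the effect is negligible.

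**Conclusion.** The declaration rule is wrong as written in both documents, probably through a drafting slip. If applied literally, it does not control the family-wise error once any effect is real. With one real effect at 90% power and four nulls, the error is about 76%, against about 3.5 to 4.7% under Hochberg. With four real effects and one null it is about 92 to 99.6%, against about 3 to 4%. These figures rest on five normal test statistics with an assumed common correlation of 0 to 0.7 and the assumed power. The logical fault shown by the two examples needs none of these assumptions. If the named procedure is programmed correctly, no error inflation follows.

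**What to change.** In SAP 7.7 and in the multiple-comparisons paragraph of Protocol 12.2, replace the declaration after step 1 with: *then it and all outcomes with smaller p-values are significant, and outcomes with larger p-values are not*, applied at each step. Confirm that the analysis program follows this rule.

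As an editorial note only, compare unrounded p-values with the exact fractions 0.05/k, printing 0.05/4 as 0.0125.

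The cost is one sentence in each document, with no new data and no extra analysis.
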